## INTRODUCTION

We urgently need tools to mitigate the impact of the COVID-19 pandemic. The proposed cluster-randomised controlled trial may provide evidence regarding a safe and cheap tool, which is already at hand, namely the oral polio vaccine (OPV).

## JUSTIFICATION

Oral polio vaccine (OPV) was developed in 1962 by Albert Sabin and consists of live attenuated polioviruses. Large-scale clinical studies of OPV for non-specific prevention of diseases were carried out in the 1960s-70s involving more than 60,000 subjects. The studies showed that OPV was effective against influenza virus infection, reducing the influenza incidence 3.8-fold on average(1, 2). More recent studies confirmed these observations on OPV. Data from a randomized controlled trial (RCT) of OPV in Guinea-Bissau, West Africa, showed that OPV-at-birth reduced infant mortality by ~32% (3). In addition, an analysis of the effect of annual / bi-annual national OPV immunization campaigns indicates that they reduce all-cause mortality by 19%, with each subsequent campaign adding a further 13% reduction(4). This means that repeated immunization has an additive effect despite protection induced by the first vaccination. Depending on initial age, it was necessary to give campaign OPV to between 68 and 230 children to prevent one death within the first 3 years of life(4). These observations were made in the complete absence of poliovirus circulation, emphasizing the non-specific nature of the broad protection induced by OPV.

In RCTs comparing OPV against Inactivated Polio Vaccine (IPV), it was found that OPV reduced the burden of bacterial diarrheal disease in infants in Bangladesh(5). In Finland, immunization with OPV was associated with less doctor-diagnosed acute otitis media than in the IPV-immunized group(6). Furthermore, a retrospective study from Denmark found that the use of OPV was associated with reduced hospital admissions for respiratory infections in children(7).

The duration of the non-specific protection induced by OPV is unknown, but long-term beneficial non-specific effects have been observed to last for many months to years after BCG vaccination(8).

We propose to assess the use of OPV to ameliorate or prevent COVID-19(2). Both polio- and coronavirus are positive-strand RNA viruses, therefore it is likely that they may induce and be affected by common innate immune mechanisms. There are multiple important advantages of OPV: a strong safety record, its low cost, and its ease of administration and availability. Over 1 billion doses of OPV is produced and used annually in more than 140 countries. A small fraction of OPV intended for the suspended polio eradication campaigns would be sufficient for the clinical trials, and provided a positive outcome, production could likely be scaled up quickly.

The risk of complications due to OPV is extremely low. Vaccine-associated paralytic polio (VAPP) develops in 1 per 3 million vaccine doses given to unimmunized individuals. Sequential use of IPV and OPV demonstrated that prior immunization eliminates the risk of VAPP. In populations with inadequate immunity OPV was also shown to generate circulating vaccine-derived polioviruses (cVDPV). However, in countries with sufficient vaccine coverage the risk is minimal: over 35 years of OPV use in the United States there was no documented case of cVDPV emergence.

An RCT of OPV against COVID-19 is currently being discussed in the US. This effort is acknowledged by the Global Polio Eradication Initiative(9).

The African population faces severe challenges due to COVID-19. As everywhere else, it is anticipated that not least the older part of the population will be at risk of severe COVID-19. Even though OPV is widely used in Africa, it is for children, and it seems unlikely that the older population have received OPV in childhood or will still benefit from any protection induced by their childhood vaccines. We therefore propose to test if a dose of OPV to older Africans above 50 years of age - presumably in the highest risk for severe COVID - may ameliorate or prevent COVID-19 and other infectious diseases. Even a partial protection could have enormous impact in a pandemic situation, while we are waiting for more specific vaccines and treatments to be invented.

If the results of RCTs with OPV are positive, OPV could be used to protect the most vulnerable populations globally (8).

## **OBJECTIVES**

To test if OPV can reduce the risk of COVID-19 among adults aged 50 years and above in an urban African setting.

Primary outcome: Mortality and severe morbidity (hospitalisation or consultations for infections) during 6 months of follow-up.

## **METHODS**

We will conduct a cluster-randomised trial of OPV vs. no OPV to 3400 adults aged 50 years and above in Bandim Health Project's study area. We will focus on the older individuals, because global figures show that they are at the highest risk for severe COVID-19, and because they will not have received OPV recently.

**Setting:** The Bandim Health Project's (BHP, [www.bandim.org](http://www.bandim.org)) Health and Demographic Surveillance System (HDSS) site follows a population of 102,000 individuals in six suburbs in Bissau, Guinea-Bissau, with home visits and through surveillance at the nearby national hospital. BHP has a long track record of conducting large-scale RCTs of vaccinations with infectious disease morbidity and mortality as outcomes. The six suburbs are divided into zones; within each zone, houses are given a unique number.

**Design:** The study will be a cluster-randomised trial of OPV. The main reason for choosing the cluster-randomised approach is to minimise the contact between the field assistant and the household.

**Randomisation:** The randomisation unit will be "house". Houses will be allocated randomly to intervention or control clusters by means of a randomly generated list of house numbers allocated to either group (<https://www.random.org/sequences/> - for an example see Appendix 1; a new list will be generated for the purpose of the RCT).

**Intervention:** The intervention treatment will be bivalent OPV (GSK), given as two drops on a sugar lump, in addition to advice regarding how to protect oneself from COVID-19. The control persons will not receive OPV, but just similar advice.

**Study population:** Eligible for participation will be adults living in BHP study area.

**Inclusion criteria:** Living in a household which has had a census visit conducted after 1 January in 2017 or later. Age above 50.

**Exclusion criteria:** Previous adverse events to OPV; Previous documented COVID-19; Acute severe infection.

**Study procedures:** In each house, an assistant will come to the house, ask for oral consent, and provide OPV and advice or just advice to all household members above 50 years of age, who are registered in our registration system and who have consented orally and in writing to participate (for participant information and informed consent form, see Appendix 2a&b+3). Their name, age, sex and ID will be registered along with as many telephone numbers as possible. A short baseline questionnaire will be filled in regarding general health including chronic diseases (Appendix 4). To maintain social distancing, no physical examination will be carried out, but the field assistant will visually assess the participants weight using a validated tool (Appendix 5). Participants will be asked for consent to being followed for mortality, hospitalisation and consultations by monthly telephone calls and registration of consultations at the health centre for 6 months.

**Follow up per telephone:** Participants will be called monthly to ascertain their vital status and health (see follow-up questionnaire, Appendix 6). In the case that a participant reports acute severe illness during an interview, the participant will be advised to seek medical advice.

All individuals are also followed through the Bandim HDSS. For all registered deaths, we will conduct a verbal autopsy(10) seeking to establish the cause of death.

**Follow-up on consultations:** If a study participant is ill, he/she will can go to the Bandim Health Project (next to the Bandim Health Centre) between 8-12 in the morning to be registered and obtain a voucher for a free consultation at the Bandim Health Centre clinic. A BHP assistant will be present with a list of study participants, to verify participation in the study, register the person with name, study ID and main cause of the consultation, and to hand out the vouchers. The Bandim Health Centre will register the patient with a study ID, and the diagnoses and treatment. The health centre will be refunded on a regular basis for consultations held for study participants.

#### **Outcomes:**

**Primary outcome:** Composite outcome of the first of death, hospitalisation for infection and/or consultation for infection at the health centre

**Secondary outcomes:** Episodes with self-reported infectious disease morbidity. Episodes with self-reported infectious disease morbidity suspected to be caused by COVID (three or more of the following: fever, cough, sore throat, extreme fatigue, loss of smell/taste). Either of the components of the composite outcome described above included repeated events.

**Statistical analysis:** Data will be analysed in Cox proportional hazards models, with time since randomization as the underlying time, to provide hazard ratios (HRs) with 95% CIs for comparison of the intervention and control groups. With the exception of the primary outcome, data will be analysed as a multiple failure time data set. Age in groups of 5 years and suburb will be adjusted for. Clustering within houses will be adjusted for.

**Sample size:** The Bandim Health Project has purchased 1700 doses of OPV. The trial will include participants until the 1700 doses have been used. With a samples size of 3400, half getting OPV, the trial can show a reduction in the combined risk of mortality (which has been around 2% in this age group in our study area) and severe morbidity after 6 months of follow-up from a total of 10% to 7.2% (i.e. a 28%

reduction) with 80% power and alpha of 0.05. Since only individuals above the age of 50 years are eligible to enter the trial, only few houses will have several participants and we expect a very limited effect of clustering.

**Explanation to participants:** Participants will be given thorough information about Coronavirus, about precautions to be taken, and about the study (Appendix 2).

**Timeline:** A Gantt diagram is presented in Figure 1.

### **Ethical considerations**

Based on previous experience the risk of side effects from OPV is extremely low. Very rarely, there may be vaccine associated paralysis in non-immune individuals (1 per 3 million vaccine doses given to unimmunized individuals), which we do not expect to encounter since most Guineans in this age group have had polio infection in childhood, they have been repeatedly exposed to vaccine viruses when campaigns have been conducted and polio vaccine is now recommended for all Guinean children. Adverse events are most often seen after the first dose in children. Individuals infected with human immunodeficiency virus (HIV), both asymptomatic and symptomatic, can be immunized with OPV(11).

All BHP contacts with families will be restricted to the minimum necessary and the recommended protective measures and physical distance will be accurately followed by field workers and household residents during essential contacts within the scope of the study.

The protocol has been approved by the Guinean Ethics Committee and will be submitted to the Danish Ethics committee for consultative approval. The trial will be registered at [clinicaltrials.gov](https://clinicaltrials.gov).

### **Dissemination of results**

As soon as the data analysis has been completed, the study report will be made available to the Center for Health Emergency Operations in Guinea-Bissau for possible use of the results. The report will also be deposited in the library of the National Institute of Public Health. The data will be published in a scientific journal and may be used for graduate work. The results of the intervention will be widely disseminated to health personnel at all levels.

1.1 Participant population

Bandim Health Project monitors the health and survival of a population of approximately 100,000 individuals through a Health and Demographic Surveillance System (HDSS) implemented across six suburbs (Bandim-I, Bandim-II, Cuntum-I, Cuntum-II, Belem and Mindara) of Bissau. For the present trial, we visited residents aged >50 years living in five of the six suburbs in the HDSS to invite them to participate. People were invited to participate, if they did not have acute current infection, signs of immune suppression (≥ 2 pneumonias in the past year, oral candidiasis, fungal skin infections) or previous confirmed COVID-19. Furthermore, individuals with paralysis or past paralyses suspected to be caused by past thrombo-embolic complications were not offered enrolment due to the risk of recurrent events and paralysis, which could be confused with paralysis due to vaccination with oral polio vaccine (OPV). All analyses will be conducted on the per-protocol population.

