1.2 Randomisation

All houses in five urban study area districts (Bandim-I, Bandim-II, Cuntum-I, Cuntum-II and Belem) were randomised to intervention or control group stratified by zone (Bandim-I: zones 1-9, Bandim-II: zones 1-8, Cuntum-I: zones 1-9, Cuntum-II: zones 2-4, and Belem zones A-E).

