1.3 Baseline Interview

Prior to enrolment a list of potentially eligible people was extracted from the HDSS databases. At the enrolment visit, information on sex and age was confirmed, and all participants were interviewed on chronic diseases, symptoms on the day of enrolment, medicine intake in the past month and admissions within the past 3 months. We aimed to have minimal physical contact. Therefore, weight was assessed using a visual scoring system, based on the field assistant's perception of the participant's bodily appearance, scoring weight from 1-10¹. The presence of a BCG and/or smallpox vaccination scar was also assessed by visual examination.

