1.6 Statistical analyses

1.6.1 Statistical model

The outcome rates will be compared by randomisation arm in Cox proportional hazards models, with time since randomization as the underlying time, to provide hazard ratios (HRs) with 95% CIs. The main results will be adjusted for age (in 5-year age-bands) and zone (based on which the randomisation was stratified). Clustering within houses will be adjusted for. With the exception of the primary outcome, data will be analysed as a multiple failure time data set. All statistical tests will be 2-tailed and $p \leq 0.05$ considered statistically significant.

Prior to implementing the trial, stories of experimental COVID-19 vaccines planned to be tested in Africa had been circulating on social media, and many perceived the OPV, which we were providing in the present trial, as one of these experimental vaccines. We have therefore encountered high refusal rates, especially in the intervention arm. As this may have resulted in baseline imbalances, we will present both the 'crude' result (only adjusted for age and zone) and adjusted results where we will adjust for background factors which affect the estimated effect of OPV on the primary outcome by more than 10%. The background factors to be investigated are presented in Box 1.

In subsequent analyses of the trial dataset, we intend to use targeted maximum likelihood estimation (TMLE) (section 2.6.2). These analyses will be reported later.

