1.6.3 Missing data

No outcome data will be imputed. However, for a particular event, we will assume that it was not caused by an infection if no information is obtained. Some dates of events may be imprecise (e.g., unknown date of consultation or only month of event known) – such dates will be allocated to the midpoint of the range of possible dates. As all individuals are followed for mortality through the HDSS, individuals whom we were not able to contact by telephone will still contribute to the assessment of the main outcome.

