2.2 Primary analysis of primary outcome

The rates of the primary outcome (a composite outcome of the first of death, hospitalisation for infection and/or consultation for infection at the health centre) within 6 months after enrolment will be compared in Cox proportional hazards models with time since enrolment as the underlying timescale.

The primary analysis of the primary outcome is described in more detail in table 1.

Table 1: Primary analysis of primary outcome

Population	Per-protocol population
Observation period	From: enrolment To: 183 days after enrolment Censoring: None
Failure definition	Death or first post-enrolment admission for infection and/or consultation for infection registered at a health centre.
Statistical tools	Cox-proportional hazards model, adjusted for the zone (stratification variable in the randomisation) and age. Robust standard error to adjust for same-house clustering.
Outline stata code	<pre>stset outdate, f(combinedoutcome=1) origin(dateenrol) enter(dateenrol) exit(dateenrol+183) stcox group b11.zone b50.agegroup b1.box1var1 b1.box1var2 ..., vce(cl house) Where [box1var1] [box1var2] etc. are the background factors from Box1 which affect the [group]-estimate by at least 10% Check of proportional hazards assumption¹: estat phtest, detail stphplot, adj(zone agegroup box1var box2var) strata(group)² stcox group, strata(zone agegroup box1var box2var) vce(cl house) /// tvc(group) tezp(_t)</pre>

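### All analyses use a per-protocol population that is never defined, and no as-allocated analysis is planned, although consent followed house randomisation and refusal was higher in the OPV arm

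*SAP*

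**What the plan says.** **Order of events.** The protocol (Methods, Randomisation) allocates houses "by means of a randomly generated list of house numbers allocated to either group". SAP 1.2 confirms that all houses in five districts "were randomised to intervention or control group stratified by zone". Consent comes afterwards. Under Study procedures in the protocol, the assistant visits the house, asks for consent, and is to "provide OPV and advice or just advice to all household members above 50 years of age" who are registered and have consented.

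**Refusal.** SAP 1.6.1 explains that OPV was widely taken for an experimental COVID-19 vaccine and says: "We have therefore encountered high refusal rates, especially in the intervention arm". It accepts that baseline imbalance may have resulted. It gives no rate for either arm.

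**Analysis population.** SAP 1.1: "All analyses will be conducted on the per-protocol population". The population row of Table 1 (SAP 2.2) reads "Per-protocol population", as do those of Tables 2-6. No definition appears in either document.

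**Planned handling.** SAP 1.6.1 gives a result adjusted for age and zone, and a second that adds the Box 1 factors that move the OPV estimate by more than 10%. A TMLE re-analysis (SAP 2.6.2) is to be reported later. SAP 2.1 plans a flowchart by allocation and a baseline description of those in the main analysis.

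**Data on people who did not enrol.** SAP 1.3: "Prior to enrolment a list of potentially eligible people was extracted from the HDSS databases". SAP 1.6.3 begins its statement on telephone non-contact with "As all individuals are followed for mortality through the HDSS".

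**The concern.** Two separate losses can occur between the randomised houses and the analysed people.

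(a) *After enrolment.* A per-protocol set normally excludes people who did not receive what they were allocated. Here that could remove someone in an OPV house who consented but did not take the vaccine. The control arm has no matching exclusion, because a control participant has no dose to miss. Without a definition, the reader cannot tell whether such people are kept, and the choice could be made after the data are seen.

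(b) *Before enrolment.* A resident who would join a follow-up study but not take OPV tends to be enrolled in a control house and lost in an OPV house. The enrolled groups can then differ in health, exposure or care-seeking. Care-seeking bears directly on the result, because a health-centre consultation is a component of the primary outcome. Covariate adjustment and TMLE deal with measured factors only, and neither Box 1 nor the TMLE covariate list contains vaccine distrust or care-seeking habit.

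At stake is whether the primary hazard ratio can be read as the effect of OPV. A larger sample does not reduce either bias.

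**Working it through.** **1. The plan's own figure.** Inputs (protocol, Sample size): 1700 per arm, 10% versus 7.2%, power 80%, alpha 0.05; two-sided per SAP 1.6.1. Schoenfeld's formula with hazard ratio 0.72:

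events = 4 × (1.960 + 0.842)² / (ln 0.72)² = 291.

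Expected events = 1700 × (0.10 + 0.072) = 292, which gives 80.1% power. The sample size reproduces and is not in dispute. It sets the scale: the target is a 28% reduction.

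**2. Bias from non-enrolment, with no OPV effect.** The documents give no refusal rates, so every input here other than 1700 per arm is an assumption. The 10% risk in acceptors is borrowed from the protocol's control risk.

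- a0, a1 = acceptance in control and OPV houses
- k = risk in the extra refusers (those who enrol only if allocated control) relative to acceptors
- Enrolled control risk: pc = 0.10 × [a1 + (a0 − a1) × k] / a0
- Enrolled OPV risk: 0.10
- Null risk ratio = 0.10 / pc
- Rejection probability: two-sided two-proportion normal test, 1700 per arm, no covariate adjustment

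Worked case, a0 = 0.85, a1 = 0.60, k = 2: pc = 0.10 × (0.60 + 0.25 × 2) / 0.85 = 12.94%, and the ratio is 10 / 12.94 = 0.77.

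| Acceptance, control vs OPV | k | pc | Null risk ratio | Rejection (nominal 5%) |
|---|---|---|---|---|
| 90% vs 80% | 0.5 | 9.44% | 1.06 | 8% |
| | 0.7 | 9.67% | 1.03 | 6% |
| | 1.0 | 10.00% | 1.00 | 5% |
| | 1.5 | 10.56% | 0.95 | 8% |
| | 2.0 | 11.11% | 0.90 | 18% |
| 85% vs 60% | 0.5 | 8.53% | 1.17 | 32% |
| | 0.7 | 9.12% | 1.10 | 14% |
| | 1.0 | 10.00% | 1.00 | 5% |
| | 1.5 | 11.47% | 0.87 | 28% |
| | 2.0 | 12.94% | 0.77 | 77% |

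The bias can go either way. It vanishes if the extra refusers carry the acceptors' risk (k = 1) or if the same kind of people refuse equally in both arms (a0 = a1).

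**3. What these figures do not measure.** They describe problem (b) only. Analysing all enrolled people by allocation leaves every row unchanged. Problem (a) cannot be sized, because neither the definition nor the number who enrolled without taking OPV is given.

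**4. What an all-listed mortality analysis could show.** Assume 1% to 2% six-month mortality (the protocol gives about 2% for this age group), a 28% effect in the vaccinated, refusers at the same baseline risk, 60% to 70% acceptance in OPV houses, and 1700 acceptors per arm. Listed people per arm = 1700 / acceptance, that is 2833 to 2429. Diluted risk = m × (1 − 0.28 × acceptance), where m is the control mortality; for m = 2% and 70% acceptance it is 1.61%. Power runs from 10% (1%, 60% acceptance) to 18% (2%, 70% acceptance). The analysis can only be supportive.

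**The case against.** The strongest reply is that the sentence in SAP 1.1 does not cause the bias in the table. OPV is given at the enrolment visit to people who have consented, so the per-protocol set may nearly coincide with all enrolled by allocation. That stands, and it is why the two problems need separate fixes. It does not excuse the missing definition.

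The SAP also discloses the refusal problem, plans crude and adjusted results, and adds TMLE. It compares outcomes by randomisation arm, and SAP 2.3 describes mortality as covering all individuals. This is fair credit. But Table 3 labels the mortality population per-protocol, and adjustment reaches measured factors only.

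A reader might infer more than the documents support:

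- *That refusal was much higher in the OPV arm.* The SAP gives no rates. It supports higher, not how much.
- *That controls had nothing to refuse.* They too had to consent, be interviewed and accept six months of follow-up, and the calculation above allows 10% to 15% control refusal.
- *That the selection will be invisible.* A flowchart by arm is planned. What is not planned is any description of those who did not enrol.
- *That the hazard ratio is known to be badly biased.* The 77% rejection needs a 25-point acceptance gap and doubled risk in refusers. The stated reason for refusal is a rumour, not illness, and at 90% versus 80% acceptance with k from 0.7 to 1.5 rejection is only 6% to 8%.
- *That an intention-to-treat relabelling would restore the randomised comparison.* It would not recover people who never enrolled.

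**Conclusion.** The concern holds in two parts. (a) The sole analysis population is undefined and no as-allocated analysis is planned; this rests on the text alone. (b) Because consent followed allocation and refusal differed by arm, even an as-allocated analysis of enrolled people is only partly protected by randomisation; this rests on the SAP's own report. The direction and size of (b) are unknown. Over the assumed range, the null risk ratio lies between 1.06 and 0.90 for a 10-point acceptance gap and between 1.17 and 0.77 for a 25-point gap, before any covariate adjustment. The larger values are comparable with the 28% reduction the trial was sized for. Part (a) can be fixed by wording. Part (b) can be examined and reported, but not removed.

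**What to change.** 1. **SAP 1.1 and Tables 1-6.** Make the primary population all enrolled eligible participants, analysed by the allocation of their house whether or not OPV was taken. Keep per-protocol as a sensitivity set with a written definition. Align the mortality population in SAP 2.3 with Table 3. *Cost:* wording and one extra model run.

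2. **Supportive mortality analysis.** Compare deaths among everyone on the pre-enrolment HDSS list by house allocation, adjusted for zone and age, with standard errors robust to house clustering. *Cost:* it appears to need no new data collection, but ethics approval must be confirmed to cover non-participants. The estimate is diluted, power is low (10% to 18% in the cases above), and the list holds only potentially eligible people, so it includes some whose clinical eligibility was never checked.

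3. **Flowchart and baseline table.** Beside the planned flowchart, compare listed-but-not-enrolled with enrolled people by arm on the variables the HDSS holds. *Cost:* one descriptive table.

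4. **Stated limitation.** Hospitalisation and consultation data were collected from participants, so the composite cannot be recovered for refusers. State that residual selection bias remains in the primary hazard ratio after adjustment and TMLE.
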